Statistical Analysis Plan for The Self-Match Study: a randomized controlled trial to assess if treatment outcome is improved if patients match themselves to treatment options

[name]^{1,2,3}, [name]^{1,2,3} and [name]^{1,2,3}.

¹Institute of Clinical Research, Unit of Clinical Alcohol Research (UCAR), University of Southern Denmark, Odense, Denmark

²OPEN, Odense Patient data Explorative Network, Odense University Hospital, Odense, Denmark.

³Psychiatric Research Unit, Region of Southern Denmark.

Contact information:

[name] (Corresponding author): [contact]

[name]: [contact]

[name]: [contact]

ClinicalTrial.gov identifier: NCT03278821. Document date: December 4, 2019.

Abstract

Background: There is growing emphasis on involving patients in their own treatment, however, research has been limited on the benefit of having patients choose their treatment from among options, in contrast to being assigned to a treatment by experts. Consequently, we designed a rigorous test of patient self-matching to determine whether it does improve retention, adherence and outcome in alcoholism treatment.

Method: The present study is conducted as a superiority randomized controlled trial. 401 consecutive patients aged 18 or more is enrolled and randomized to either self-matching or expert-matching to one of five different treatment approaches. The following instruments was administered at intake to provide standardized measures of alcohol problems: Addiction Severity Index, Time Line Follow Back, WHO quality of life questionnaire, NEO Five-Factor inventory-3 and Personal Happiness Form. Methods of statistical analysis are described, including the handling of missing data.

Outcome: For each outcome measure, two analyses will be conducted. Intention-to-treat analyses (ITT) will be carried out with all patients, irrespective of whether they completed the interventions or were re-interviewed. Regarding incomplete data, multiple imputations will be used together with ITT. Completer analyses will also be carried out with patients who complete their respective interventions.

Primary outcome: Decrease in number of monthly excessive drinking days 6 months after initiation of treatment.

Secondary outcomes: (1) Compliance. (2) Quality of life.

Trial registration: ClinicalTrial.gov identifier: NCT03278821. Registered September 12, 2017

Key words: Alcohol addiction, binch drinking, Alcohol treatment, informed choice, randomized controlled trial.

Background

International attention to involve patients in their own treatment in most medical fields, including addiction treatment, is increasing [1, 2]. The main point is that treatment regimens should encourage that patients have an active role in treatment planning [3-6]. In alcohol treatment, Project MATCH [7] and the UKATT Research Team [8], has tested the paternalistic approach to treatment planning and found that the best 'guesses' of some of the field's most experienced alcoholism treatment researchers in two nations were little better than chance when it came to choose the best treatment approaches for patients. In sum, experts matching patients to treatment based on patient characteristics is doubtful for improving treatment outcome[9] [10].

The opposite approach is to allow patients to match themselves, that is to make an informed choice from a menu of evidence-based treatment options. In large treatment regimens where more than one treatment option can be provided it would be feasible to allow patients to choose for themselves. Patient preference is increasingly being considered as good practice in healthcare, leading to implementation of shared decision making and informed choice, which is feasible when patients can be given a fair description of the options open to them and permitted to make an informed choice as to which treatment they prefer.

It is, however, still not clear if these approaches improve treatment outcome. A systematic review of the literature on shared decision making in treatment of substance use disorder [11] found that only 3 out of 25 trials found a significant effect when treatments were matched to patients preferences. The result should, however be interpreted with caution due to heterogeneity of the included studies.

To our knowledge, research is limited when it comes to clarify the benefit of having patients, suffering from alcohol addiction, freely choose their treatment approach from among options. Therefore, as a part of the RESCueH-studies[12], this randomized clinical trial will compare the efficacy of patient self-matching versus treatment-as-usual expert matching.

Purpose and hypotheses

The primary purpose of this randomized controlled trial is to determine if patient self-matching to psychotherapy treatment methods improves 1) drinking outcome, 2) compliance and 3) quality of life for patients being treated for alcohol problems compared to assignment as usual, which is by the means of expert matching.

A priori hypotheses

1. Patients who choose their own treatment will show significantly greater reductions in alcohol consumption (measured by number of days with excessive drinking) at follow-up, when compared to patients assigned to treatment by expert match.
2. Patients who choose their own treatment method will show significantly better compliance in treatment (measured by retention) when compared to patients assigned to a specific treatment method by expert match.

Material and methods

Study Design

The study is conducted as a superiority randomized controlled trial. 401 consecutive patients aged 18 or more are enrolled. All new patients fulfilling the inclusion criteria receive oral and written information about the study. Patients are randomized to either expert matching (algorithm) or self-matching. See the study protocol for more information on referral routines[13].

Study procedures

Information about the study is presented when the potential participant first attends the treatment center. If the patient needs treatment for withdrawal symptoms, the information is not given until those symptoms are sufficiently treated.

The baseline interview is divided into two sessions to avoid fatigue during a long assessment. This is already standard procedure in the clinic for everyone receiving treatment regardless of participation in this study. Upon written and oral

consent patients are randomized to either choosing their own treatment among five options or being assigned to one of these options by means of an algorithm[14] and expert opinion. Patients participating in the study will be re-interviewed 6 months after initiation of treatment.

Getting patients to participate in studies and getting a high follow-up rate is usually an obstacle in research, thus we have designed the study routines as similar as possible to the usual assessment routines in the participating treatment institution. The only difference for those participating in this study is the 45-minute follow-up interview. To ensure a high follow-up rate we collect phone number, e-mail and home address on patients and their next of kin. If patients decide to be anonymous, we underline the importance of their responsibility to contact the treatment center 6 months after treatment start.

Randomization and blinding

Patients are assigned to conditions by REDCap (Research Electronic Data Capture) from Open (Odense Patient Data Explorative Network), a computer-based randomization system. The interviewer in charge of the first baseline interview will activate the randomization, when the patient has agreed to participate in the study. The patient witness' the randomization and the result are revealed immediately.

A case report for each participant will be prepared and labeled with participant number. All case reports will be stored in a locked storage inaccessible to the therapists, who are to remain uninformed of how patients were assigned to treatment. Patients are urged not to reveal their group assignment.

Data

The following instruments will be administered to provide standardized measures of alcohol problems, quality of life and personality traits:

- Addiction Severity Index (ASI) is an assessment tool for addiction problems [15].
- Time Line Follow Back (TLFB) is an assessment tool for measuring drinking days the last 30 days [16].
- WHO quality of life 26-item questionnaire (WHOQOL-BREF) [17].

- NEO Five-Factor inventory-3 (NEO-FFI-3) is a tool for measuring personality traits [18].
- Personal Happiness Form (PHF) is a tool for assessing well-being [19].

These validated and widely-used instruments will allow direct comparisons with mainstream clinical trials.

Statistical analyses and sample size

A multiple regression model will be used to model percent of days with drinking/excessive drinking. If the model validation shows that Gaussian multiple regression does not fit due to severely non-normal data, a multiple quantile regression model will be used instead. Both modeling approaches allow for inclusion of additional explanatory variables. A two-sided alternative will be used with a significance level of $p=0.05$. We expect that proportion of patients assigned to the five treatments will differ between the two groups; hence, type of treatment, sociodemographic data and problem severity will be integrated in the analysis as explanatory variables.

Power calculation

To our knowledge no similar experimental studies have been conducted. The power calculation is therefore estimated from what clinicians' regard to be a clinically meaningful difference in outcome. A study by Miller and Manuel [20] found that clinicians estimated the difference between two treatment methods to be meaningful for implementation in daily practice if the continuous outcome measures (e. g. number of days with excessive drinking) were halved. The power calculation is based on the number of days with excessive alcohol abuse over the last 30 days after 6 months of treatment.

Currently, patients at the participating outpatient clinic drink on average excessively 5.7 days ($SD=9.7$) over the last 30 days after 12 months of treatment. With the new methods for assigning treatment to patients, we seek to halve the number of days with excessive drinking to an average of $5.7/2 = 2.85$ days, i.e. a reduction of 2.85 days. We assume the standard deviation will be the same for the reduced number of days. Most likely, it will be smaller since less than zero days of excessive drinking is impossible, i.e. the method is conservative. As stated by Miller & Manuel [20] this power calculation is based on practitioners' judgment of a meaningful difference in outcome, rather than statistical significance based on other studies. By this approach, a total sample of 200 patients in each group is needed to have 90% power of detection a difference of this magnitude using a 0.05% level of statistical significance (Figure 2).

Sensitivity analyses

Complete case and worst-case computation will be carried out.

Interim analyses and stopping rule

An Independent Data Monitoring Board was assigned to carry out interim analyses. In case of significant and clinically relevant difference the study will be terminated due to ethical responsibility to provide the best treatment possible.

Start of data analyses

Data analyses will start primo January 2020.

Level of confidence and *p* values

A confidence level of 95% and *p* value of 0.05 is assigned.

Missing data

Incomplete follow-up data are assumed to be missing at random (MAR) and will be addressed by the MICE (multivariate imputation by chained equations) method of multiple multivariate imputation. Appropriate auxiliary variables will be included in the imputation model, the resulting datasets will be analyzed separately, and results will be combined using the rules of Rubin.

Outcome measures

For each outcome measure, two analyses will be carried out:

1. Intention-to-treat analyses (ITT) will be carried out on all patients, irrespective of whether they completed the interventions or were re-interviewed. Regarding incomplete data, multiple imputations is used together with ITT but there will be some caveats.
2. Completer (on-treatment) analyses will be carried out on patients who completed the respective interventions.

Results will be published regardless of our findings.

Primary outcome:

Number of excessive drinking days 6 months after initiation of treatment.

Secondary Outcomes:

1. Compliance measured by retention. At 6 months follow up the number of sessions attended is measured.

2. The four dimensions of Quality of life as measured by WHOQOL.

Table 1. Demographics and baseline data.

	Self-Match	Expert match (TAU)	Significance level
Demographics			
Current age mean (SD)			
Male			
Currently cohabiting or married			
Full or part time employment			
Annual income Mean (SD)			
Education (>high school)			
Treatment related to AUD and substance use			
Previously received AUD treatment			
Previously received SUD treatment			
Currently suffering from SUD			
Use of alcohol			
Number of heavy drinking days last 30 days			
Number of drinking days last 30 days			
Overall amount of alcohol consumption last 30 days			
Quality of Life			
Physical domain (sum score)			
Psychological domain (sum score)			
Social domain (sum score)			
Environment domain (sum score)			

Table 2. Follow up data

	Self-Match group	Control Group	Significance level
Follow up rate			
Percentage completed follow up			
Drinking outcome			
Heavy drinking days last 30 days			
Number of drinking days last 30 days			
Overall alcohol consumption last 30 days			
Retention			
Compliance (drop out)			
Average number of sessions completed			
Quality of Life			

Physical domain (sum score)
Psychological domain (sum score)
Social domain (sum score)
Environment domain (sum score)

Table 3: Treatment success of selfmatch compared to expert match. Treatment success defined as 50% reduction in heavy drinking days.

	Heavy drinking days		Number of drinking days		Overall consumption		Compliance (drop out)		Number of sessions completed		QoL physical domain		QoL psychological domain		QoL social domain		QoL environment domain	
	OR	CI	β	CI	β	CI	β	CI	β	CI	β	CI	β	CI	β	CI	β	CI
Expert-match																		
Self-match																		
Intercept																		

Trial status

The second version of the protocol was accepted the 17th of November 2016. The study was accepted by the Regional Scientific Ethical Committee for Southern Denmark the 24th of March 2017. Recruitment began 22nd of May 2017 ended the 5th of April 2019.

Trial registration: ClinicalTrial.gov identifier: NCT03278821

Declarations

Ethics approval and consent to participate

The Study was presented for the Regional Scientific Ethical Committee for Southern Denmark, who decided that the study did not need formal approval from the committee. Reference number: S-20170027. All procedures in the study are in accordance with the second Declaration of Helsinki.

Both oral and written information will be given to patients by the person who undertakes first baseline interview. Patients must sign informed consent document if they want to participate in the study.

All appointments in Center for Alcohol Treatment Odense are situated in private rooms with quiet and calm atmosphere and there will be no interruptions.

Availability of data and materials

All data collected in the study will be treated and stored strictly confidentially in REDCAP, OPEN. The datasets generated and/or analyzed during the current study are available from the corresponding author on reasonable request.

Competing interests

[name] (PI), [name] and [name] are employees of the University of Southern Denmark and Region of Southern Denmark. [name] is employed at the psychiatry of Region Syddanmark. None of researchers have competing interests to declare.

Funding

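### The SAP leaves two choices about the primary variable open: change versus 6-month level, and excessive versus any drinking days

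*SAP*

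**What the plan says.** The SAP describes the main drinking variable in several places.

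- Abstract, Primary outcome: "Decrease in number of monthly excessive drinking days 6 months after initiation of treatment". This reads as a change from baseline.
- A priori hypotheses, hypothesis 1: self-matched patients are to show "greater reductions in alcohol consumption (measured by number of days with excessive drinking) at follow-up". This also uses the language of change.
- Outcome measures, Primary outcome: "Number of excessive drinking days 6 months after initiation of treatment". This is a level at follow-up.
- Power calculation: "The power calculation is based on the number of days with excessive alcohol abuse over the last 30 days after 6 months of treatment". This is again the 6-month level.
- Statistical analyses and sample size, the only sentence that names a dependent variable for the model: "A multiple regression model will be used to model percent of days with drinking/excessive drinking". If the Gaussian fit fails, "a multiple quantile regression model will be used instead".
- Table 3: heavy drinking days are reported as an odds ratio, with "Treatment success defined as 50% reduction in heavy drinking days".

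The explanatory variables are type of treatment, sociodemographic data and problem severity. Problem severity is not defined, and the baseline number of excessive drinking days is not named. No sentence says which form carries the primary test.

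**The concern.** The same label, primary outcome, stands over a decrease in one place and over a 6-month number in another. Without adjustment for baseline, these two have different estimates and standard errors in the same data. The model sentence then joins two drinking variables that answer different clinical questions.

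Fixing the primary variable is the SAP's own task. The document is dated December 4, 2019. Recruitment ended on 5 April 2019, follow-up is at 6 months, and analysis is due to start in January 2020. Most or all outcome data therefore probably existed when it was written (an inference; the SAP does not say so). A wording gap at that stage leaves room for a favourable result on one form to be presented as the planned primary result, with a sentence of the SAP to support it.

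**Working it through.** **Inputs from the SAP (Power calculation; Statistical analyses):** difference 2.85 days, SD 9.7 in both arms, 200 per arm, two-sided 0.05.

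**Assumptions, because the SAP gives no figure:** baseline SD also 9.7; correlation ρ between baseline and 6-month counts of 0.2 to 0.6; correlation of 0.5 to 0.85 between excessive and any-drinking days at 6 months; normal test statistics; complete follow-up; no covariates.

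**1. The plan's own figure.** Standard error for the count = 9.7 × √(2/200) = 0.97, and 2.85/0.97 = 2.938. Power = Φ(2.938 − 1.96) = 83.6%. Power of 90% needs 244 per arm. The stated 200 for 90% is reproduced only by a one-sided 5% test (199 per arm). That is a separate error; the comparisons below use 83.6%.

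**2. Percent of excessive days.** The timeline follow-back window is 30 days, so percent = count × 100/30. The difference becomes 9.5 points and the SD 32.3 points. Their ratio is unchanged, so the p-value and the 83.6% power are unchanged too.

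**3. Unadjusted decrease.** SD = 9.7 × √(2(1 − ρ)); power = Φ(2.85/(SD × 0.1) − 1.96), where 0.1 = √(2/200).

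| ρ | SD of decrease | Power, decrease | Power, count |
|---|---|---|---|
| 0.2 | 12.27 | 64.2% | 83.6% |
| 0.3 | 11.48 | 70.0% | 83.6% |
| 0.5 | 9.70 | 83.6% | 83.6% |
| 0.6 | 8.68 | 90.7% | 83.6% |

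The two forms have equal power at ρ = 0.5. Below that the count is stronger, above it the decrease.

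**4. False-positive rate if the better result may be chosen.** With equal SDs, the two test statistics (taken with the same sign) correlate at √((1 − ρ)/2), that is 0.63 at ρ = 0.2 and 0.50 at ρ = 0.5. By simulation under no effect:

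- count or unadjusted decrease: 8.6% to 9.1%;
- count, unadjusted decrease or any-drinking count: 10.8% to 13.0%;
- excessive or any-drinking count only, with no change score: about 7.5% to 9.1%.

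The last line shows that the slash matters even if change versus level is settled.

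**5. Baseline count as a covariate.** Let Y be the 6-month count and B the baseline count. Regressing Y − B on arm and B gives the same arm coefficient and standard error as regressing Y on arm and B; only the coefficient of B falls by 1. For the decrease B − Y the arm coefficient merely changes sign. The residual SD is 9.7 × √(1 − ρ²), which gives power of 85.1% at ρ = 0.2, 92.4% at 0.5 and 95.7% at 0.6.

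**6. Forms with no computable power.** The SAP gives no mean or SD for any-drinking days and no rate for a 50% reduction, so nothing follows for either.

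**The case against.** The best defence is that the SAP is less divided than it looks. The formal definition, the power paragraph and the follow-up table all use the 6-month level. The power paragraph itself calls the difference between the arms a reduction, so the change language elsewhere may only mean fewer days than the comparator. No passage defines baseline minus follow-up as the dependent variable. Problem severity may include baseline excessive days, and then change and level coincide. Any-drinking days are never called primary, and the tables list them on their own row, so the slash may only mean that the same model serves each drinking variable.

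Much of this is fair, and it makes the 6-month count of excessive days the likeliest intention. It does not settle the matter. The abstract puts a decrease under the primary outcome label, problem severity is undefined, and the model sentence does not separate its two variables.

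A reader might also infer more than the document supports:

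- *Three incompatible versions.* Not so: percent of excessive days is a rescaled count.
- *A power statement that fits only one version.* It is written for the count, but it fits percent of excessive days equally.
- *A false-positive rate of up to about 16%.* That needs a fourth endpoint, a decrease in any-drinking days, which the SAP states nowhere.
- *A measured error rate for the planned model.* The figures assume no covariates, whereas the plan is a covariate-adjusted regression.

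**Conclusion.** The point holds as two unresolved choices about the primary variable: change or 6-month level, and excessive or any drinking. If the first is left open, the false-positive rate is about 9%; if the any-drinking count may also serve, it is about 11% to 13%, against a nominal 5%. At the stated difference and SD with 200 per arm, power is 84% for the count and between 64% and 91% for an unadjusted decrease.

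These sizes are illustrative. They rest on assumed correlations, a baseline SD equal to the follow-up SD, normal statistics and no covariates. They show what the wording would permit, not that any choice has been or will be made on the results. If the baseline count is in the model, change versus level stops mattering and only the slash remains.

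**What to change.** Name one primary variable throughout: the number of excessive drinking days in the 30 days before the 6-month interview. Analyse it with the baseline count of excessive drinking days as a named covariate, so that change and level lead to the same treatment test.

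- **Abstract:** drop the reference to a decrease, so that it matches Outcome measures.
- **Hypothesis 1:** state that it is tested by the baseline-adjusted difference between arms in this count.
- **Model sentence:** replace the percent and the slash with this count, and list the baseline count among the covariates.
- **Any-drinking days and the Table 3 odds ratio for a 50% reduction:** label each as secondary or exploratory.

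Naming the covariate is the step that matters. Merely choosing the unadjusted count would lose power against an unadjusted decrease if ρ exceeds 0.5. Under the assumptions above, the adjusted analysis is at least as powerful as either.

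The cost is a few wording edits before analysis starts. No new data are needed: Table 1 already lists heavy drinking days over the last 30 days at baseline, taken here to be the same measure as excessive drinking days. The SAP should confirm that the two terms mean the same.

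### An undefined normality check can swap the powered difference in means for quantile regression at an unnamed quantile, so the primary estimand and its power are not fixed in advance

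*SAP*

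**What the plan says.** Under Statistical analyses and sample size, the SAP opens with the main model: "A multiple regression model will be used to model percent of days with drinking/excessive drinking". The next sentence gives the exception: "If the model validation shows that Gaussian multiple regression does not fit due to severely non-normal data, a multiple quantile regression model" is to replace it. The test is two-sided at 0.05. No diagnostic or cut-off is given for the exception, and no quantile is named anywhere in the SAP.

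The Power calculation section works only with means. Clinic patients average 5.7 excessive drinking days in 30 (SD 9.7, at 12 months), and "we seek to halve the number of days with excessive drinking to an average of" 2.85. On the spread it says: "We assume the standard deviation will be the same for the reduced number of days". It concludes that 200 per group gives 90% power.

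The outcome itself is worded in several ways:

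- Outcome measures: "Number of excessive drinking days 6 months after initiation of treatment", with no summary measure.
- Abstract: "Decrease in number of monthly excessive drinking days 6 months after initiation of treatment".
- A priori hypotheses: the self-matched group "will show significantly greater reductions in alcohol consumption (measured by number of days with excessive drinking) at follow-up".
- Table 3: an odds ratio column for heavy drinking days, under the title phrase "Treatment success defined as 50% reduction in heavy drinking days".

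**The concern.** A difference in means and a difference at a quantile are different quantities, and each quantile is a different one again. The SAP powers the first and permits any of the others, depending on how someone judges a model check once the data are in. The reported effect, and whether it is significant, could then turn on that judgement and on the quantile chosen.

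The stated power does not carry over to a quantile. Nor does a quantile difference say whether the 2.85-day target in the mean was met. Because the outcome is already described as a level, a decrease and a responder odds ratio, the switch adds one more candidate to an endpoint that is not single.

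**Working it through.** **Inputs.** From the Power calculation section: control mean 5.7, SD 9.7, target mean 2.85, 200 per group. From the Data section: drinking is measured over the last 30 days, so the outcome lies between 0 and 30. Modelling percent of days instead of days only rescales it.

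**1. The plan's own figure.** The standard error of the difference is 9.7 × √(2/200) = 0.97, and 2.85/0.97 = 2.938.

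- Two-sided 0.05: power = Φ(2.938 − 1.960) = 0.836 (0.834 with the t distribution). For 90% power, n = 2 × (1.960 + 1.282)² × 9.7²/2.85², which gives 244 per group.
- One-sided 0.05: power = Φ(2.938 − 1.645) = 0.902, and n = 199.

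So 200 per group at 90% is reproduced only with a one-sided test, although the SAP states a two-sided one. Either way, the figure concerns a difference in means.

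The assumed SD of 9.7 in the improved arm cannot occur at mean 2.85 on 0-30 days. The maximum is √(2.85 × 27.15) = 8.80, which gives power of 0.868.

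**2. Is the switch likely to be triggered?** These results use only the mean, the SD and the 0-30 range.

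- A normal distribution would put Φ(−5.7/9.7) = 27.8% of patients below zero days.
- Skewness: E[X²] = 9.7² + 5.7² = 126.58. By Cauchy-Schwarz, E[X³] ≥ 126.58²/5.7 = 2810.96. The third central moment is then at least 2810.96 − 3 × 5.7 × 126.58 + 2 × 5.7³ = 1016.8. Dividing by 9.7³ = 912.67 gives at least 1.11. On whole days, a linear programme gives a range of 1.115 to 2.102.
- Median: the same linear programme gives a minimum P(X ≤ 3) of 0.440 and a minimum P(X ≤ 4) of 0.514. The control median is therefore at most 4.
- Share with zero days: anywhere from 0 to 74%. Zero-heavy data are plausible but not proven.

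**3. Illustration A: zero-heavy data.** Beta-binomial out of 30, with controls at mean 5.7 and SD 9.7. The halved arm has mean 2.85 and an assumed SD of 6.86 (9.7/√2) or 8.0. There are 200 per arm and no covariates.

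| | Control | Halved, SD 6.86 | Halved, SD 8.0 |
|---|---|---|---|
| P(0 days) | 0.587 | 0.734 | 0.839 |
| Median | 0 | 0 | 0 |
| 75th percentile | 7 | 1 | 0 |

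| Comparison | Power, SD 6.86 | Power, SD 8.0 |
|---|---|---|
| Means (Welch) | 0.928 | 0.892 |
| 75th percentile (bootstrap) | 0.765 | 0.997 |

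Both sample medians are 0 in 99.2% of trials. The 75th-percentile power moves by a few points with the bootstrap details.

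**4. Illustration B: fewer zeros.** Controls have the same moments, and half of the drinkers become abstinent.

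| Control P(0) | Median | 75th percentile | Mean (Welch) |
|---|---|---|---|
| 0.10 | 0.34 | 0.18 | 0.92 |
| 0.20 | 0.85 | 0.32 | 0.90 |
| 0.30 | 0.99 | 0.53 | 0.91 |
| 0.45 | 0.27 | 0.80 | 0.92 |

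Which quantile does better depends on the shape. The mean hardly moves.

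**5. Does skewness require the switch?** Shape A was rerun with covariates (severity, age, sex, treatment type) and complete data. Least squares with HC3 errors had type I error of 4.5-5.0% and power of 85-92%. In the same setting the median coefficient was within 0.5 day of zero in 99-100% of trials, and the 75th-percentile coefficient averaged −3.5 to −5.3 days.

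**The case against.** The hierarchy is written down in advance: a first-choice model, one fallback, a reason for switching, a test level and classes of covariates. Only a trigger value and a quantile are missing, and a reader may take the median as the default. The switch depends on model fit and not on the treatment effect or its p-value, and nothing here shows that the two-stage procedure inflates the type I error. The normality trigger concerns residuals of an adjusted model at 6 months, whereas the bounds above concern raw 12-month values. The quantile power figures rest on assumed shapes, and the adjusted runs used complete data although multiple imputation is planned. Level and change also give the same treatment coefficient if baseline drinking days is a covariate.

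Much of this stands as a limit on the claim. The switch is likely, not certain; the quantile figures are illustrations; inflated false positives are not claimed. The level-versus-change point depends on whether the SAP's problem severity covariate includes baseline days, which it does not say. The power shortfall and the Table 3 odds ratio exist with or without the switch.

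The core is untouched. The two missing details are the ones that decide what is estimated. Reading the fallback as the median does not rescue it, since in zero-heavy data the median can hide the very halving the trial was sized to find.

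**Conclusion.** The concern holds. The SAP powers only a difference in means, yet lets an unquantified check replace it with a quantile difference whose quantile is never named. Neither the primary estimand nor its power is fixed in advance.

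From the plan's own moments, with no assumption on shape beyond the 0-30 range, control skewness is 1.1-2.1 and the control median is at most 4. Across the illustrated shapes with a true halving, power ranges from essentially none to 99% at the median and from 18% to 99.7% at the 75th percentile, against 89-93% for means. Those ranges rest on the assumed distributions, treated-arm SDs and complete data. The 12-month planning figures are also taken as a guide to 6 months. At about 200 per arm, a comparison of means with robust errors kept its type I error in the shapes tried, so skewness does not compel the switch. This should be corrected before analysis.

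**What to change.** - Delete the switch. Make the adjusted difference in mean excessive drinking days at 6 months the single primary analysis, with heteroscedasticity-robust or bootstrap standard errors.
- State one sensitivity analysis in advance: an over-dispersed bounded-count model (beta-binomial or quasi-binomial out of 30 days) that reports the marginal mean difference.
- Make any quantile regression secondary, with its quantile named now.
- State that the primary outcome is the follow-up level, and reconcile this with the Abstract, the A priori hypotheses and the odds ratio column for heavy drinking days in Table 3.

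If the sponsor prefers to keep a conditional rule, the minimum is a numeric trigger, a named quantile, and a target and power on that scale.

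The cost is SAP wording, a robust-variance option and one extra sensitivity model. No new data are needed. The downside is slightly more analysis work and the loss of primary status for a quantile result.
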